### **Understanding Smoking among Tribal College Students**

(P20-NIMHD: PIs: [name] & [name]) We are conducting a longitudinal web-based survey of tribal college students at two tribal colleges on behavioral risk factors including smoking. We have found that approximately 40% of tribal college students are current smokers (Freshmen = 36%, Sophomores = 40%, Juniors = 45%, Seniors = 27%).

*This study demonstrates our team's ability to successfully work with tribal colleges and recruit tribal college students to participate in research studies.*

### **Summary**

In conclusion, these preliminary studies have: 1) demonstrated our successful collaboration and commitment to the AI/AN community; 2) shown our experience in conducting smoking cessation studies; 3) confirmed the cultural-appropriateness of ANBL; 4) shown that the ANBL approach is feasible and acceptable in the AI/AN population; 5) proven our ability to successfully recruit AI/AN smokers for a pilot cessation study; 6) demonstrated our ability maintain excellent retention rates (approximately 80%); and 7) demonstrated preliminary success of smoking abstinence with ANBL. Collectively, these results position us well to undertake this randomized clinical trial that we will now propose in the next section.

## **III. Benefits and Risks of Research**

### **Benefits**

The participants will have the opportunity to benefit by making behavioral changes in their smoking or by stopping smoking. Participants who stop smoking will experience invaluable

health benefits, and family members of participants who stop smoking would be expected to benefit from reduced exposure to second-hand smoke. Participants will receive several things to help them quit smoking, including the opportunity to receive free NRT, Chantix® and NRT or Zyban®, materials to assist with quitting smoking, web-based culturally tailored smoking cessation counseling. Participants will have an opportunity to receive \$90 in gift cards for recognition of time and trouble spent participating in this study. Additionally, participants will receive incentives valued at approximately \$30 per person. Participants will be informed that disbursement of the incentives is not contingent on their smoking status.

Despite over two decades of intensive tobacco control efforts, about 23% of Americans continue to smoke. Native Americans carry a disproportionate burden of tobacco use and related mortality. Racial disparities in tobacco use and cessation translate into higher rates of mortality from tobacco-related disease. Thus, to address the tobacco use epidemic and its consequent health impact, there is an urgent need to test interventions for tobacco dependence, to improve delivery by individualizing treatment based upon smokers' needs, and to reduce barriers to smoking cessation in underserved populations. This study will assess whether a culturally targeted smoking cessation program with choice of pharmacotherapy is effective for smoking cessation among AI tribal college student smokers. The knowledge to be gained from this research could potentially change the types of treatment offered to AI college student smokers. The risks involved in gaining this knowledge are reasonable given the potential impact of the knowledge to be gained on smoking cessation treatment.

## **Risks**

Most of the risks involved in the study relate to adverse events related to study medication. Chantix and bupropion are both approved by the Food and Drug Administration as an aid for smoking cessation. The most common adverse events associated with bupropion are headache, insomnia, rhinitis, dry mouth, and anxiety. Bupropion is associated with an increased risk (1/1000 at 300 mg/day) of seizures (GlaxoSmithKline, unpublished data). We will minimize this risk by screening out and preventing participants from using bupropion who are also currently using any additional form of bupropion, psychoactive medications, nicotine replacement therapy, fluoxetine, clonidine, buspirone, or doxepin in the past 30 days and those with: self-reported alcohol dependence within the past year; history of seizures or head trauma; history of bulimia or anorexia nervosa; pregnant (as measured by over the counter pregnancy test kit for women of child-bearing age only) or contemplating pregnancy; breast feeding; myocardial infarction in the past 30 days, and use of other forms of tobacco in the past 30 days. The most common adverse events associated with Chantix are nausea, changes in dreaming, constipation, gas, and/or vomiting. The FDA recently required new boxed warning for both these medications: people who experience any serious and unusual changes in mood or behavior or who feel like hurting themselves or someone else stop taking the medication. Chantix has no clinically meaningful drug interactions based on drug characteristics and clinical experience with the drug to date (Pfizer).

All participants requesting prescription medications, Chantix or Bupropion will be screened and medically cleared by the on-the-ground primary care physician. [name] will continue his role as reviewing study physician. [name] will provide secondary review of all screeners, and intake materials to make sure there are no contradictions to pharmacotherapy. We have a long track record of [name] reviewing all medication screeners and study documents on

participants in our tobacco cessation studies. We are comfortable with individual's self-report, mostly because we have done this successfully for years in our other tobacco cessation studies.. For Participants at a Tribal college: Participants who choose to take Chantix will also be monitored by Tribal clinic, will correspond with [name] about participants taking Chantix. All Participants will be prompted to discuss any side effects prior to starting each web-session and will be given the study office phone number (24-hour coverage) to contact study staff and/or the investigators to report adverse events. On – the - ground physician will decide if they need to directly communicate with participants when participants initiate or while they are taking medications. Our staff will also have weekly contact with participants (via our web-based communication system). [name] will provide secondary review and communicate with the on-the-ground physician or participant if need clarification on any screener responses, if the participant reports side-effects from study medications, if the participant has an Adverse Event (AE) that could be due to study or study medication related, or if the participant requests to speak with a study physician. We will follow the NIH guidelines for reporting adverse events to the Human Subjects Committee. Any problems needing medical attention will be referred to [name] (consulting physician) and the patient's personal physician. The study medication will be discontinued in patients who become pregnant, report use of any other medications that contain bupropion (e.g., Wellbutrin), or develop a contraindication. Patients will be instructed not to smoke cigarettes during treatment. Women of child bearing age who are participating in the program and requesting to use Chantix or Zyban will agree to use a form of birth control during the course of the study.

Alternatives to participating in the study are to quit cold turkey, use other smoking cessation programs, purchase nicotine gum or patches from the pharmacy, obtain a prescription for bupropion or other smoking cessation products from their physician, or continue to smoke. Other risks for participating in the study are minimal and include those associated with the inconvenience of completion of several questionnaires, email follow-up assessments, and the inconvenience of logging onto the internet for web-based counseling sessions.

All participants in the study will be quitting smoking. Risks to all participants will be minimized through frequent monitoring through the web chat portal where participants can chat with study personnel. All participants will be given detailed instructions on how to use either the nicotine replacement therapy, Chantix or bupropion prior to distributing the cessation aids. Finally, all participants will be given a 24 hour monitored telephone number to contact in case of adverse reactions to any of the cessation aids that they are using.

Furthermore, KUMC will be in weekly contact with a clinician or nurse at the Tribal campus health center to review any adverse events or suspected adverse events. We will also be specifically asking participants about adverse events on a weekly basis (via our web –based communication system) and follow-up with phone calls to review anything reported. The following questions will be asked from participants using web-based system to report any adverse events from medications:

- “Have you had any side-effects from your pharmacotherapy this week?”
- “Have you had any urgent or emergent visits to the doctor or a hospital for health problems this week?”

- “Have you had any new unexpected health problems this week that we have not talked about?”

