#### **IV. Inclusion/Exclusion Criteria**

##### **Eligibility**

The eligibility criteria listed below will be assessed at the recruitment visit.

Inclusion Criteria	Exclusion Criteria

 
◆ Age 18 years or older
 
◆ Currently enrolled at a Tribal college
 
◆ Have a valid telephone number and email address
 
◆ Willing to participate in all study components
 
◆ Willing to be followed-up for 6 months
 
◆ Self identifies as American Indian or Alaska Native
 
◆ Is a current smoker – self defined
 
	
 
◆ Planning to leave the college within next 6 months
 
◆ Medically ineligible as a result of screening questions
 

Medical Exclusion Criteria

For overall participation
 
 
◆ Medically ineligible as a result of screening questions
 
◆ Participant under the age of 18 years
 

For NRT (Patch, gum, lozenge):
 
 
• History of severe eczema or any serious skin problem if requested nicotine patch
 
• History of severe allergic reaction to the nicotine patch or other skin adhesives
 
• History of heart attack in the last 2 months
 
• Currently experiencing frequent angina or chest pain related to heart
 
• Currently experiencing signs and symptoms of peptic ulcer
 
• Currently receiving medications for rapid or irregular heart beat
 
• Currently experiencing signs and symptoms of severe, uncontrolled high blood pressure
 
 
For Chantix:
 
 
• Pregnant or breast feeding or planning to become pregnant in the next 6 months
 
• Currently using nicotine replacement therapy (NRT)
 
• History of suicide attempt in the past 12 months
 

- History of thoughts of suicide in the past 12 months
- History of thoughts of harming others in the past 12 months

For Zyban:

- Pregnant or breast feeding or planning to become pregnant in the next 6 months
- History of seizure disorder or head trauma
- History of severe allergic reaction to Zyban (also known as Wellbutrin, Bupropion)
- History of eating disorder, such as anorexia or bulimia, which is overeating and throwing up
- Currently taking Wellbutrin, Zyban or any other medications that contain bupropion

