- History of alcohol or substance abuse in the past year
- Current excessive alcohol consumption defined as 14 or more alcoholic drinks per week and / or binge drinking ( 5 or more drinks on one occasion) 2 or more times in the past month
- Use of MAO inhibitors, such as Nardil, tranylcypromine, phenelzine, or Parnate
- Reported use of illegal drugs (opiates, cocaine, narcotics, or other stimulants such as diet pills)
- Use of psychoactive medications, such as fluoxetine, doxepin, clonidine, or buspirone
- Use of benzodiazepines, such as Xanax, Valium, Ativan, Klonopin in the past 2 weeks

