**Anticipated Flow of Participants:**

Telephone Eligibility Screening Interview		
↓		
In-Person Randomization Visit (n=300)		
←      ↓      →		
Web-based weekly		
Sessions	I – ANBL (n=150)	I – FV (n=150)
1	Preparing to quit, pharmacotherapy/nrt, why do people smoke	Assessment of Risk for Heart Disease, pharmacotherapy/nrt
2	Cigarette smoking and Native people, Quit smoking date	Increasing fruit and vegetable consumption, Quit smoking date
3	Coping with Withdrawal	Physical activity
4	Traditional use of tobacco	High blood pressure
5	Stress reduction and relaxation techniques, traditional meditation techniques	Salt and sodium intake
6	Weight management, Healthy American Indian foods, exercise	High Cholesterol
7	Friends and family and quitting smoking, social support	Maintaining healthy weight
8	Staying quit – congratulations Long term maintenance	Low cost healthy eating – fruits and vegetables
Email reminders will be sent before each session so that participants will log in at the appropriate time		
12	End of pharmacotherapy treatment, feedback of program	End of program, feedback

Email reminders will be sent before each session so that participants will log in at the appropriate time		
Month 6	Assessment for current smoking status	Assessment of current smoking status

(Detailed descriptions of the weekly I-ANBL web materials are included in the appendix: will be adapted to integrate tribal college student issues identified during Phase 1 of the study)

- Telephone Screening Intake:** Research Assistants will review inclusion/exclusion criteria, smoking status and basic information about the program. We will not exclude participants who use other forms of recreational tobacco (eg – smokeless tobacco) because, based on our preliminary data, we would be excluding eligible participants if we did so. In addition, community members have encouraged us to be more inclusive for acceptability of the research in the community and make the inclusion criteria less restrictive. Therefore, we will examine use of other tobacco products in a secondary analysis. We estimate screening intake to take 10-15 minutes.

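### Three conditions that the protocol's Risks section says bar bupropion (NRT use, recent myocardial infarction, other tobacco use) are missing from the Section IV Zyban exclusion list

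*Protocol*

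**What the plan says.** Section III (Risks) quotes a seizure risk of 1/1000 at 300 mg/day for bupropion. It says this will be minimized by "screening out and preventing participants from using bupropion who are also currently using any additional form of bupropion, psychoactive medications, nicotine replacement therapy" and it goes on to further conditions, ending with "myocardial infarction in the past 30 days, and use of other forms of tobacco in the past 30 days". The wording is a commitment, and the list is not offered as examples.

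Section IV (Medical Exclusion Criteria) gives separate lists for NRT, Chantix and Zyban. The three conditions are placed there as follows:

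- Current NRT use is listed under Chantix only.
- A heart attack is listed under NRT only: "History of heart attack in the last 2 months".
- Other tobacco use is listed under no medication.

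In Section V, the telephone screening step says of trial entry: "We will not exclude participants who use other forms of recreational tobacco". The in-person visit step has everyone who asks for medication complete the medical screener for that drug, which the study physician reviews. The screeners themselves are not in the document.

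**The concern.** Section IV is where staff will look to decide who may have which drug, and it is the natural source for a drug-specific screener. If the screener follows Section IV, it will not ask about NRT, recent infarction or other tobacco for someone requesting bupropion. A person whom Section III says must be kept off the drug could then pass.

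The affected people can be in the trial. Users of other recreational tobacco are knowingly enrolled, and the trial itself supplies NRT. Section III also says the study medication is stopped if a contraindication develops. Without a settled list, it is unclear whether starting NRT or other tobacco while on bupropion meets that condition.

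At stake is the consistency of a stated medication-safety rule. The efficacy comparison is not involved.

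**Working it through.** No arithmetic beyond counting applies. The inputs are the bupropion sentence in Section III (Risks) and the Zyban list in Section IV, which continues across a page break with no sign of redacted or missing text. Psychoactive medications and the four drugs named with them are counted as one bar.

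| Bar on bupropion in Section III | Counterpart in the Section IV Zyban list |
|---|---|
| Another bupropion product | Yes |
| Psychoactive medications, with four named drugs | Yes, the same four: "Use of psychoactive medications, such as fluoxetine, doxepin, clonidine, or buspirone" |
| NRT | **None** (current use is under Chantix only) |
| Alcohol dependence, past year | Yes, within alcohol or substance abuse |
| Seizures or head trauma | Yes |
| Bulimia or anorexia | Yes |
| Pregnant or contemplating pregnancy | Yes |
| Breast feeding | Yes |
| Myocardial infarction, past 30 days | **None** (heart attack is under NRT only) |
| Other tobacco, past 30 days | **None** (under no drug) |

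Count: 10 bars, 7 with a counterpart, 10 − 7 = 3 without.

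Read the other way, the 11 Zyban items are pregnancy or breast feeding, seizure or head trauma, bupropion allergy, eating disorder, other bupropion products, alcohol or substance abuse, excessive drinking, MAO inhibitors, illegal drugs, psychoactive medications and benzodiazepines. None of them can be read to include NRT, infarction or other tobacco.

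Take an enrolled student who also uses smokeless tobacco and asks for bupropion. Telephone screening admits the student, no Zyban item applies, and Section III bars the drug. A participant with an infarction in the past 30 days is in the same position: the NRT list stops NRT, the Zyban list does not stop bupropion, and Section III does.

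The general exclusion for medical ineligibility on screening does not close the gap, because it depends on which questions the screener asks.

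**The case against.** The strongest reply is that this is an omission and not an opposing rule. Nothing in the protocol says that such people may have bupropion, and the two lists could be applied together, with a bar in either one sufficient. Every request also needs clearance by the on-site physician, a secondary review for contraindications and a prescription (Sections III, V and VI). The unseen screener may already follow Section III. All of this lowers the practical risk. However, no text says that the lists are cumulative, none of the safeguards states the three criteria, and screening relies on self-report. A reviewer cannot act on a question that was not asked.

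A reader might infer more than the documents support:

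- **That seizure screening is materially weakened.** Section III presents its list as seizure prevention, but the seizure risk factors named in Section VI do not include any of the three conditions. No increase in seizure risk can be claimed.
- **That the lists conflict equally in the other direction.** Section IV does hold items that Section III does not spell out. But the Section III bar on psychoactive medications plausibly covers benzodiazepines and arguably MAO inhibitors, and a risk narrative shorter than the eligibility list is not a contradiction.
- **That the infarction windows clash.** The 30 days in Section III concern bupropion and the 2 months in Section IV concern NRT. Different drugs may have different windows.
- **That the look-back for psychoactive medications conflicts.** The Section III sentence begins with current use and ends with the past 30 days, so the reach of that phrase is uncertain.
- **That enrolling other-tobacco users contradicts Section III.** That rule is about trial entry. It only makes the missing drug-level rule relevant.
- **That the screener is known to be deficient.** It is not shown.

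**Conclusion.** The point holds for the three omitted conditions. Section III commits to keeping NRT users, people with an infarction in the past 30 days and recent users of other tobacco off bupropion. The Zyban list in Section IV contains none of them, so following Section IV alone would not carry out that commitment.

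The size is 3 of the 10 bars stated in Section III. The number of participants affected cannot be derived from the documents. The same medications are offered to both arms and the sample size calculation uses no medication input, so the primary analysis and power are not affected. This is an inconsistency in a safety rule that an amendment should settle.

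The conclusion assumes that the Zyban list is complete as shown. It makes no assumption about what the screener contains.

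**What to change.** 1. Make the Zyban list in Section IV the governing list for bupropion, and have the Risks text in Section III refer to it instead of keeping a second list.
2. Add current NRT use and myocardial infarction in the past 30 days to that list.
3. Have the study physician decide whether the other-tobacco bar stands, knowing that the trial enrols such users. If it stands, add it to Section IV with its 30-day window. If not, delete it from Section III.
4. Confirm that the bupropion screener asks about every retained item, and revise it only if it does not.

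The cost is a wording amendment and, if needed, one screener revision. A few fewer people may be cleared for bupropion; the documents give no basis for a number. Keeping the other-tobacco bar would withhold the drug from some enrolled participants, which is why that item needs a clinical decision and should not be added by default.

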### **Plans for Assuring Compliance with Requirements Regarding the Reporting of Adverse Events (AE).**

The pharmacotherapy that will be used in this study has been approved by the Food and Drug Administration for aid in smoking cessation treatment. The adverse events associated with the TNP are few and mild and include skin irritation at the patch site and mild increases in heart rate and blood pressure. Adverse events related to nicotine gum and lozenge use are generally few and mild and can include hiccups, sore mouth and jaw, indigestion, headache, nausea, and insomnia. Studies have shown that varenicline is well tolerated, with few and mild adverse effects. The most common varenicline-related adverse effect is nausea, which is reported to be mild to moderate. Varenicline use will be monitored by the patient's primary care physician. The most common adverse effects associated with bupropion are dry mouth and insomnia. Subjects may also rarely complain of confusion, anorexia, or dizziness. Bupropion is also associated with a 1/1000 risk of seizures at the dose that will be used in this study. Factors that may increase the risk of seizures include: a history of head trauma, seizures, CNS tumors, excessive use of alcohol or cocaine, withdrawal from alcohol or benzodiazepines, and use of certain other drugs, including antipsychotics, antidepressants, theophylline, and systemic steroids. All patients will be screened for risk factors for seizures prior to recommending use of bupropion. Bupropion will only be provided to participants who have received a prescription from their primary care physician.

Participants will be prompted to discuss any adverse effects with their primary care physician or, if they do not have a primary care provider, with [name] or the on-site clinician who will work with [name]. Both subjects and physicians will be given the study office phone number (24-hour coverage) to contact study staff and/or investigators to report adverse events.

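### The weekly web questions do not ask about new medicines or pregnancy, although the stop rule for study drug turns on them; the gap is small and partly mitigated

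*Protocol*

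**What the plan says.** The Risks part of Section III sets a stop rule: study medication is to be "discontinued in patients who become pregnant, report use of any other medications that contain bupropion (e.g., Wellbutrin), or develop a contraindication". The same part prints three weekly questions and states their purpose: "The following questions will be asked from participants using web-based system to report any adverse events from medications". The first asks about side effects of the pharmacotherapy and the second about urgent or emergency care. The third is open: "Have you had any new unexpected health problems this week that we have not talked about".

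The protocol also states several safeguards.

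- The on-the-ground "physician will decide if they need to directly communicate with participants when participants initiate or while they are taking medications".
- Women of child-bearing age who request Chantix or Zyban "will agree to use a form of birth control during the course of the study".
- For varenicline, "Participants who choose to take Chantix will also be monitored by Tribal clinic", and Section VI adds monitoring by the primary care physician.
- For bupropion, Section VI says: "Bupropion will only be provided to participants who have received a prescription from their primary care physician".
- For everyone, the Risks part describes weekly contact between the coordinating centre and a campus health-center clinician or nurse, a web chat portal, telephone follow-up of anything reported, and a 24-hour telephone line.

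**The concern.** A stop rule acts only when someone learns that its condition has been met. Here the bupropion-product condition is worded so that it applies when the participant reports such use, and the Risks part says openly that the team is content to rely on self-report. Under self-report, the question put to the participant is the main means of detection. The questions printed for weekly use do not mention medicines or pregnancy.

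What is at stake is participant safety, chiefly for those on bupropion. The adverse-event part of Section VI lists circumstances that may raise the seizure risk on this drug, among them "excessive use of alcohol or cocaine, withdrawal from alcohol or benzodiazepines, and use of certain other drugs, including antipsychotics, antidepressants". Drugs of the kinds named there can be started after the entry screen. A second bupropion product can be too, and the stop rule singles that out. Pregnancy matters for both prescription drugs, since it is an exclusion for each.

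**Working it through.** No arithmetic applies. The check sets each stop condition against each printed question, then looks for any other place where the condition would be checked during treatment.

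**1. Stop conditions against the weekly questions**

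| Stop condition | Side effects | Urgent or emergency care | New unexpected health problem |
|---|---|---|---|
| Pregnancy | Not asked | Not asked | May be volunteered; not named |
| Another bupropion product | Only if it causes a noticed side effect | Only if it comes with an urgent visit | Only if the reason for the prescription is itself new and is reported |
| New contraindication | Only if felt as a side effect | Yes, if it leads to urgent care (a seizure, chest pain) | Yes, if it is a health condition; not if it is a new medicine |

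None of the three conditions is asked about directly. A contraindication that shows itself as an illness is reasonably covered. One that consists of taking a new medicine is not.

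**2. Entry checks**

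- The pregnancy test is described in the Risks part, as part of screening for bupropion.
- The medical screener is completed by those requesting pharmacotherapy (Section V, Individual In-Person Visit). The study physician reviews it before the first session.
- The seizure-risk screen comes before bupropion is recommended (Section VI, reporting of adverse events).
- Under Pharmacotherapy in Section V, participants collect a one-month supply once the on-the-ground physician has cleared them.

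All of these are stated for the start of treatment. None is said to be repeated, whereas the flow table runs pharmacotherapy to week 12.

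**3. Other routes during treatment**

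- The automatic inquiry in Section VI starts from an urgent or unexpected medical encounter. A routine appointment is neither.
- The weekly call with the campus clinic reviews actual or suspected adverse events.
- Direct contact by the on-the-ground physician is at that physician's discretion.
- The chat portal and the 24-hour line are open to every participant, but they depend on the participant raising the matter.
- Clinic and primary-care monitoring during treatment is stated for Chantix. For bupropion, the stated step is the prescription before supply.

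**4. A case that passes through**

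A participant on study bupropion is given Wellbutrin at a routine visit by a different prescriber, for a long-standing complaint, and feels no side effect. All three answers are truthfully no. No urgent encounter has occurred, so no inquiry starts, and the stop rule is not triggered although its condition is met.

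**The case against.** The strongest reply is that nothing here is contradictory. The weekly questions are introduced as an adverse-event prompt, not as the means of applying the stop rule, and the protocol does not say that nothing else is asked. The consent form, the screeners and the instructions given when drug is handed out are not reproduced, and these are usual places to tell participants to report a pregnancy or a new prescription. The clearance wording under Pharmacotherapy can fairly be read as clearance before each monthly supply. The safeguards listed above reach all participants in some form, and a duplicate from the same prescriber would probably be noticed.

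Most of this stands, and it keeps the point small. It does not remove it: no stated safeguard is a re-check of medicines or pregnancy during treatment.

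A reader might infer more than the text supports, in four ways.

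- **That participants have no protection during treatment.** The safeguards above show otherwise.
- **That alcohol, drug use and every Zyban exclusion should be re-screened at each resupply.** The number of resupplies is not stated, clearance may already be tied to supply, and the protocol does not say whether a contraindication in the stop rule means every item on the exclusion list.
- **That the quoted 1/1000 seizure risk sizes the problem.** It is the risk on bupropion in general, not the excess due to an undetected contraindication, and no multiplier is given.
- **That newly starting a benzodiazepine is one of the seizure factors in Section VI.** The factor named there is withdrawal; benzodiazepine use is a Zyban exclusion.

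The assessment schedule also has no row for other medicines or pregnancy. It is labelled preliminary, so no weight is put on that.

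A practical objection is that web sessions run in weeks 1 to 8 and week 12, with only individual emails in weeks 9 to 11. This fails, because weekly web-based adverse-event questioning is stated separately from the sessions in the Risks part, under Pharmacotherapy and in Section VI.

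**Conclusion.** The point holds as a minor participant-safety improvement. Two named stop conditions, pregnancy and another bupropion product, are not prompted for by the weekly questions the protocol prints, and no repeat of the entry screen during treatment is stated. The gap is least covered for bupropion users. It is smaller for pregnancy and for Chantix users, given the birth-control agreement, the open third question and the stated Chantix monitoring.

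The number of participants affected cannot be estimated, since the protocol gives no uptake by drug, no co-medication rate and no pregnancy rate. The conclusion assumes that the forms not shown do not already carry the missing prompt; if they do, the change is one of consistency only. The primary endpoint, sample size and analysis are not touched.

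**What to change.** Keep the stop rule and the reliance on self-report. For participants holding Chantix or bupropion, add one item to the weekly web questions in the Risks part, asked until pharmacotherapy ends at week 12. It should ask whether, since the last report, they have started any new medicine (naming bupropion products such as Wellbutrin) or become pregnant. Send any yes to the on-the-ground and study physicians by the route Section VI already sets for adverse-event reports.

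The cost is one extra question a week, so no more than 12 answers per participant on these drugs, and physician time only when the answer is yes. The wording would need community and IRB approval, which the Implementation Plan already provides for when the protocol is modified.
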